Given the clinical relevance of NPS in ADRD, the equivocal results of the therapeutic resources available to address it, and the emerging evidence of safety and efficacy of tDCS in ADRD, our proposal aims to test the acceptability, safety and efficacy of home-based tDCS for the treatment of NPS in ADRD. Home-based tDCS circumvents critical problems observed in previous trials (16), including the need of multiple visits to medical centers for tDCS application, allowing a more intensive application (e.g. 5 x per week) for long periods.

Objectives

Objectives	Outcome Measures
Primary objective To assess acceptability and safety of providing tDCS to ADRD patients with behavioral symptoms.	Acceptability will be evaluated using Likert scale (from 0 [strongly disagree] to 10 [strongly agree]) to answer ten affirmatives regarding the use of home-based tDCS. Safety will be assessed with a questionnaire about side effects that include itching, burning, headache, fatigue, and dizziness. Acceptability scale will be applied on Week 2, 4, 6 and 12. Side effects questionnaire will be applied on Week 2, 4 and 6.
Secondary objectives To assess the efficacy of tDCS for ADRD on clinical outcomes, mainly behavioral symptoms.	Behavioral symptoms and cognitive measures evaluated through validated tools: NPI, bDAS, CSDD, MMSE. NPI will be applied on Baseline, Week 2, 4, 6 and 12, while bDAS, CSDD and MMSE will be applied on Baseline, Week 6 and Week 12.

Study Design

We will carry out an open-label study to evaluate home-based active tDCS for AD and behavioral symptoms. There will be no randomization. All eligible patients will receive exactly the same treatment. All participants (n=20) will receive active tDCS with a constant current intensity of 2mA. Anodal tDCS will be applied to the left dorsolateral prefrontal cortex, while cathodal electrode will be positioned on the right dorsolateral prefrontal cortex. Caregivers will help setting up and administering tDCS for participants with AD at home. tDCS will be applied for 30min at an intensity of 2mA, with

30 s ramping up and down.

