Following recommendations in the statistical literature analyses we will proceed using parallel frequentist and Bayesian statistical inference. Frequentist analyses will provide conventional interpretation of the relationships between predictors and outcomes: the probability of the data, given the null hypothesis. Bayesian analyses will incrementally update specified prior information regarding effects to directly yield the probability of an alternative hypothesis. Bayesian analyses will employ weakly informative priors as a default (e.g., for regression coefficients: $\sim N[\mu=0, \sigma^2=100]$). Sensitivity analyses using optimistic and pessimistic, skeptical priors will evaluate prior assumptions. Assessing the convergence of Bayesian analyses on the posterior distributions via Monte-Carlo Markov chain (MCMC) will use diagnostic evidence including effective sample size and scale reduction factors. Evaluation of posterior distributions will permit statements regarding the probability that effects of varying magnitudes exist, given the data, even with a small sample size. Frequentist analyses will evaluate all *a priori* models at the $\alpha=0.05$ (two-tailed) significance level and will employ false discovery rate (FDR) to control for Type I error across any exploratory or *post hoc* analyses. Bayesian models will be evaluated via PP threshold guidelines in the literature suggesting that PP = 75% to 90% indicates moderate evidence, PP = 91% to 96% indicates strong evidence, and PP = 97% or above indicates very strong to extreme evidence. Bayesian analyses do not conceptualize Type I error in the same way as frequentist analyses due to formally calibrating probability in the prior distribution (as opposed to long-run probabilities, as in

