frequentist analyses) and are less influenced by multiple comparisons in general due to observation of the Likelihood Principle. The current Bayesian analyses stipulate posterior probabilities ≥ 0.75 (equivalent to a Bayes factor = 0.33 or 3.0) that parameter estimates are greater or less than zero provide a minimum threshold of evidence to emphasize the value in discerning effects in a small study. The Bayesian inferential paradigm can provide probabilistic estimates of effects irrespective of sample size. Power considerations focus on identifying change over time from baseline to end-of-treatment. Notably, the Bayesian analyses will provide the primary inferential results; thus considerations for the frequentist analyses are limited by the small sample size and provided solely as due diligence. Given alpha = 0.05, a sample size N = 20 provides 80% power to detect an effect size Cohen's d = 0.66.

Study Population

A maximum of 20 persons with ADRD and clinically-meaningful behavioral symptoms will be enrolled in the study. This sample size is set to maximize the number of participants that may be enrolled over the time period of the proposal assuming a credible average recruitment rate, given the financial resources.

Inclusion criteria. Participants who are 60 years or old will be considered eligible if they: (1) have ADRD and clinically-meaningful behavioral symptoms, (2) have a caregiver willing to participate in the study, (3) can speak and read English, (4) have stable doses of medications for at least one month. The diagnosis of ADRD will be verified by the investigators based on Mini-Mental Status Exam score (between 14 - 25) (22, 23). Clinically-meaningful behavioral symptoms will be determined by the Neuropsychiatric Inventory (NPI), and defined as a total score ≥ 10 arising from at least two domains (24, 25).

Exclusion criteria. Participants will be excluded if they have: (1) any unstable concurrent medical conditions, (2) history of brain surgery, seizure, or intracranial metal implantation, (3) current alcohol/substance use disorder.

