Safety will be assessed with a questionnaire about side effects that include itching, burning, headache, fatigue, and dizziness (21). The most common side effects of tDCS reported in the literature are very mild and include tingling, burning sensation, and skin redness, while other less common side effects may include headache, sleepiness, dizziness, and difficulty concentrating (22-23). Although rare, a possible adverse event of tDCS is the occurrence of skin lesions or small skin burns on the site where electrodes touch the skin (24-25). The side effects questionnaire will be applied on Week 2, 4 and 6 to assess the incidence and frequency of side effects in our recruited sample. We expect that the occurrence of side effects will be similar to the frequencies reported in the scientific literature, demonstrating that home-based tDCS is a safe and feasible intervention to be used on the management of ADRD patients with behavioral symptoms.

Secondary Outcome

The main efficacy measure will be change on the Neuropsychiatric Inventory (NPI) score (26), the best-validated tool for measuring NPS in dementia patients. This 12-item informant-based interview is a widely accepted measure of NPS in dementia. The NPI consists of a detailed evaluation of the following 12 neuropsychiatric domains: hallucinations, delusions, agitation/aggression, depression, anxiety, irritability, disinhibition, euphoria, apathy, aberrant motor behavior, change in night-time sleep behavior, and changes in appetite and eating (27). Each NPS domain is rated according to its severity (0-3) and frequency (0-4) (28). NPS will be assessed at baseline, during treatment (weeks 2, 4 and 6) and 6 weeks post-treatment. Our hypothesis is that patients receiving tDCS will demonstrate lower NPI scores at the end of treatment.

Other clinical outcome measures will include: (1) total score on the Brief Dimensional Apathy Scale (bDAS) (29); (2) depressive symptoms as assessed by the

Cornell Scale for Depression in Dementia (CSDD) (30); (3) cognition as evaluated by the Mini-Mental State Examination (MMSE), which includes memory, language, praxis and orientation tasks, yielding a global cognition score ranging 0 to 30, with higher scores indicating better performance (31). Our hypothesis is that all participants receiving treatment will demonstrate lower scores on the bDAS and CSDD, and higher scores on the MMSE at the end of treatment.

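### The Likelihood Principle does not protect the primary Bayesian inference from multiplicity: with no true change, the chance that at least one of the four Week 6 efficacy contrasts reaches PP ≥ 0.75 is about 41% to 68%

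*Combined protocol and SAP*

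**What the plan says.** All of the inferential rules are in the Sample size section of the combined protocol and SAP. It states that "the Bayesian analyses will provide the primary inferential results" and that the frequentist work is there only for completeness. The minimum evidence rule is "posterior probabilities ≥ 0.75 (equivalent to a Bayes factor = 0.33 or 3.0) that parameter estimates are greater or less than zero", and the grading is "PP = 75% to 90% indicates moderate evidence, PP = 91% to 96% indicates strong evidence", with a top tier from 97%.

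On multiplicity, the Bayesian analyses "are less influenced by multiple comparisons in general due to observation of the Likelihood Principle". No Bayesian adjustment, joint model or order of testing follows. On priors, "Bayesian analyses will employ weakly informative priors as a default"; the example is a normal prior with mean 0 and variance 100 for each regression coefficient. Optimistic and skeptical priors are planned as sensitivity analyses, without values. On the frequentist side, every a priori model is tested at two-sided 0.05, and the plan "will employ false discovery rate (FDR) to control for Type I error across any exploratory or" post hoc analyses.

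Under Study Procedures, Secondary Outcome, NPI change is named the main efficacy measure, with lower scores expected at the end of treatment. For the other scales, treated participants "will demonstrate lower scores on the bDAS and CSDD, and higher scores on the MMSE at the end of treatment". The Objectives table and Table 1 schedule NPI at Weeks 2, 4, 6 and 12, while "bDAS, CSDD and MMSE will be applied on Baseline, Week 6 and Week 12".

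**The concern.** The Likelihood Principle concerns what the observed data say about a parameter. It does not govern how often the largest of several posterior probabilities exceeds a fixed value. A Bayesian analysis gains protection against multiplicity from its prior, by shrinking effects towards each other or towards zero. With a separate, nearly flat prior for each coefficient, the PP is close to one minus the one-sided p-value, so a set of PPs carries the same multiplicity as a set of p-values.

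The plan has four efficacy hypotheses, a low minimum threshold, no rule on which scale carries the efficacy statement, and a sentence suggesting that the number of comparisons matters less here. A report could then feature whichever scale crossed 0.75, and its reader would have no means of judging how easily that happens by chance. There is no control arm to act as a check.

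**Working it through.** **Inputs from the documents.** N = 20; one arm; PP tiers at 0.75, 0.91 and 0.97; default prior variance 100; four scales with end-of-treatment hypotheses; two-sided alpha 0.05; power stated for change from baseline to end of treatment.

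**Assumptions.** Complete, normally distributed change scores with true mean change zero. The documents give no correlations, so between-scale values of 0 to 0.8 are shown.

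**1. The plan's own figure.** For a paired t-test with d = 0.66 and n = 20, the noncentrality is 0.66 × √20 = 2.952, with 19 degrees of freedom and critical value 2.093. Power is 0.799, which reproduces the stated 80%. The power statement therefore concerns one within-person contrast.

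**2. One contrast.** With a near-flat prior, PP = F(t), where F is the t distribution function on 19 degrees of freedom and t is the mean change divided by its standard error. Under no change PP is uniform, so P(PP ≥ c) = 1 − c in the hypothesised direction:
- 25% at 0.75
- 9% at 0.91
- 3% at 0.97

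**3. Four Week 6 contrasts, independent.** P(at least one) = 1 − c⁴:
- 1 − 0.75⁴ = 0.684
- 1 − 0.91⁴ = 0.314
- 1 − 0.97⁴ = 0.115

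**4. Four Week 6 contrasts, correlated.** Simulated null trials of n = 20, hypothesised direction:

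| Between-scale correlation | PP ≥ 0.75 | PP ≥ 0.91 | PP ≥ 0.97 |
|---|---|---|---|
| 0 | 68% | 32% | 12% |
| 0.3 | 59% | 27% | 10% |
| 0.5 | 52% | 24% | 9% |
| 0.8 | 41% | 18% | 7% |

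The plan's rule is worded for either direction. Read that way, the 0.75 figure is 80% to 94%. The one-directional figures are used here because only those would be read as benefit.

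**5. Does the default prior help?** A prior variance of 100 multiplies the t statistic by about √(100/(100 + SE²)). Assume a between-visit correlation of 0.6.
- With an NPI standard deviation of 15, the change SD is 15 × √(2 × 0.4) = 13.4, the SE is 13.4/√20 = 3.0, and the factor is √(100/109) = 0.96.
- With a standard deviation of 25, the change SD is 22.4, the SE is 5.0, and the factor is √(100/125) = 0.89.

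With these NPI values and standard deviations of 4 to 8 on the other scales, the four-contrast figure at correlation 0.3 is 58% to 59%, which is essentially unchanged. The NPI-only figure moves from 25% to 23% or 24%.

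**6. Frequentist counterpart, four Week 6 contrasts.** If independent, P(any p < 0.05) is 1 − 0.95⁴ = 0.185 two-sided and 1 − 0.975⁴ = 0.096 in the hypothesised direction. At correlation 0.8 these fall to 12% and 6%.

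**7. If every scheduled visit were also read.** The timetable contains 4 + 3 × 2 = 10 post-baseline contrasts. For between-scale correlation 0.3 to 0.8 and between-visit correlation 0.5 to 0.7, the 0.75 figure is about 59% to 81%. The lower end treats the between-visit correlation as applying to change scores. Applied to raw scores with a shared baseline, the lower end is about 65%.

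**The case against.** Several points on the other side are sound, and they set limits on what can be claimed.

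**Ten contrasts.** A reader might infer from the timetable that ten contrasts will each be judged. The documents do not say so. The four hypotheses and the power statement all concern the end of treatment, and the Statistics section plans multilevel models with possible spline terms rather than a separate contrast per visit. Weeks 2, 4 and 12 carry no stated hypothesis and may fall under the exploratory FDR provision on the frequentist side. The family the documents support is four contrasts at Week 6; the ten-contrast figure is conditional.

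**How likely.** A reader might also infer that a false signal is likely at any tier. It is more likely than not only at the 0.75 tier, and only for correlations up to about 0.5. Higher correlation is plausible, because the NPI domains include depression and apathy and so overlap with CSDD and bDAS.

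**Wording.** The plan says less influenced, and in general. It does not claim that multiplicity has no effect or that no allowance is ever needed. It also grades 0.75 as moderate and calls it a minimum, not proof of efficacy.

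**Mitigation.** NPI is already ranked as the main measure, and skeptical priors are planned. The PP rule is nevertheless not confined to NPI, and the skeptical priors have no values and no role in any decision.

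**Stakes.** Efficacy is a secondary objective in a small open-label study. Acceptability is summarised descriptively and safety by the incidence and frequency of side effects, so neither depends on these thresholds.

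**Conclusion.** The concern holds for the four end-of-treatment hypotheses. The reason the plan gives is not a valid ground for treating multiple comparisons as less of a problem, and nothing else in the plan supplies protection: the default prior does not pool, no gatekeeping is stated, and FDR does not apply to the PPs. With no true change and n = 20, the chance of at least one favourable PP ≥ 0.75 is 41% to 68% over between-scale correlations of 0.8 down to 0. It is 18% to 32% at the strong tier and 7% to 12% at the top tier.

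These figures assume complete, normal change scores and a near-flat prior. They leave out regression to the mean, which could raise the NPI rate further because entry requires an NPI total of at least 10 and there is no control arm. They do not show that the plan commits to judging ten contrasts, or that the primary objective is compromised. The matter should be corrected, but it bears only on how secondary efficacy results are read.

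**What to change.** 1. In the Sample size section, delete the appeal to the Likelihood Principle as a reason for making no allowance for multiple comparisons.
2. State that any efficacy statement rests only on NPI total, baseline to Week 6. The plan already names NPI as the main measure and focuses on the end of treatment.
3. Label the other scales and visits exploratory, and report all of them together whatever their PP.
4. State beside the results that even the single NPI contrast has a 25% chance of PP ≥ 0.75 in the hypothesised direction when nothing has changed (9% at 0.91, 3% at 0.97). Restricting the claim removes the family-level problem but not the leniency of the 0.75 threshold.

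Two other remedies are weaker. Extending FDR to more p-values would leave the PPs, which are the primary inference, untouched. A hierarchical model across the four scales would give real shrinkage, but it treats apathy, depression, cognition and total NPI as exchangeable, which the documents do not justify.

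The cost is SAP wording and a few lines in the report, with no new data or participants. The downside is that bDAS, CSDD and MMSE results can no longer be presented as stand-alone evidence.

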NPI will be applied on Baseline, Week 2, 4, 6 and 12, while bDAS, CSDD and MMSE will be applied on Baseline, Week 6 and Week 12.

Sociodemographic and Clinical (health history, use of medication and life habits) *data* (gender, age, marital status and education) will be collected at the baseline.

Assessment	Baseline	Week 2	Week 4	Week 6	Week 12
Medical History Questionnaire	X				
MMSE (Secondary outcome)	X			X	X
NPI (Secondary outcome)	X	X	X	X	X
bDAS (Secondary outcome)	X			X	X
CSDD (Secondary outcome)	X			X	X
tDCS experience questionnaire (Primary outcome)		X	X	X	X
Side effects questionnaire (Primary outcome)		X	X	X	

Table 1. Timetable for Collection of Data

Data and Safety Monitoring

Data will be collected from 20 human participants, and all information will be de-identified in order to protect their confidentiality. All clinical information will be stored in dedicated files at UT Health Department of Psychiatry and Behavioral Sciences. The data generated in this project will be presented at national or international conferences and published in a timely fashion.

Statistics

Statistical modeling will primarily use generalized linear modeling (GLM) with multilevel components (GLMM) for correlated observations. Potentially nonlinear relationships between predictors and outcomes will be evaluated via inclusion of polynomial or spline effects. Continuous, dichotomous, and count-distributed data will utilize linear, logistic, and Poisson/negative binomial regression, respectively (each with a canonical link function). Evaluation of distributional assumptions will use residual plots, formal statistical tests, and posterior predictive checking. Violations of assumptions will be addressed via transformation, robust estimation, stratification, and/or coefficient scaling

where appropriate. Statistical analyses will be performed using the R statistical computing environment via packages lme, rstan, and brms.

Ethics/Protection of Patient Confidentiality

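### NPI total of 10 or more is both the entry filter and, probably, the baseline for the one-arm NPI efficacy measure, and no medication follow-up is described, so NPI change should be reported as uncontrolled change

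*Combined protocol and SAP*

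**What the plan says.** **Entry.** Under Study Population, Inclusion criteria, clinically meaningful behavioral symptoms are determined by the NPI and "defined as a total score ≥ 10 arising from at least two domains".

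**Outcome.** Under Objectives, the secondary objective is "To assess the efficacy of tDCS for ADRD on clinical outcomes, mainly behavioral symptoms". Under Study Procedures, Secondary Outcome: "The main efficacy measure will be change on the Neuropsychiatric Inventory (NPI) score", and "Our hypothesis is that patients receiving tDCS will demonstrate lower NPI scores at the end of treatment". Study Design describes one open-label arm: "There will be no randomization".

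**Schedule.** "NPI will be applied on Baseline, Week 2, 4, 6 and 12" (Study Procedures, and the same in Table 1). Table 1 has no screening column.

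**Evidence rule.** The Sample size section makes the Bayesian results the primary inference. It states that "PP = 75% to 90% indicates moderate evidence", and that posterior probabilities of at least 0.75 "that parameter estimates are greater or less than zero provide a minimum threshold of evidence". The same section plans skeptical and optimistic priors and statements about effects of different magnitudes. Multilevel models are planned under Statistics.

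**Medication.** The inclusion criteria require doses to have been stable for a month or more before entry. Study Procedures lists medication use among the data taken at baseline, and Table 1 marks the Medical History Questionnaire at baseline only. No later recording is described.

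**The concern.** Patients chosen because a fluctuating score was high tend to score lower when measured again, whether or not they are treated. If the score that admits a patient is also the baseline from which change is measured, the expected change is a fall, and a fall is what the plan hypothesizes. With one arm, nothing separates it from an effect of tDCS. The planned priors, magnitude statements and multilevel models all act on total change from baseline.

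This goes further than the usual limit of a one-arm study, because the plan attaches evidence labels to the result and the lowest label is easily earned. A modest fall from selection could be reported as moderate evidence on the efficacy objective.

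Medication is a separate issue with a different mechanism. Psychotropic changes during the 12 weeks could move the NPI either way. As the plan is written, the analyst would not know that they had happened, and they may be hard to recover later.

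**Working it through.** **1. The plan's own figure.** Inputs from Sample size: N = 20, alpha 0.05 two-tailed, d = 0.66. For a paired t-test the noncentrality is 0.66 × √20 = 2.95 with 19 df, which gives power of 79.9%. The stated 80% reproduces. The calculation treats all baseline-to-end change as signal.

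**2. The change that meets the evidence rule.** With a nearly flat prior, the posterior for the mean change is approximately t with 19 df. The N(0, 100) prior alters this little. The observed d needed is the t(19) quantile divided by √20 = 4.472:

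| PP | t(19) quantile | observed d |
|---|---|---|
| 0.75 | 0.688 | 0.154 |
| 0.91 | 1.392 | 0.311 |
| 0.97 | 2.000 | 0.447 |

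With no true change and no selection, PP ≥ 0.75 for benefit is reached in 1 − 0.75 = 25% of trials. That 25% belongs to the threshold, and only the excess over it belongs to selection.

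**3. Is the qualifying score the baseline?** One pre-treatment NPI is scheduled. Costs and Compensations counts five paid assessments, which matches the five columns of Table 1. Both facts make a single score plausible. Against that, Table 1 is a data-collection timetable and not a screening schedule, and the assessment figure cited in Study Design is not visible here. The premise is an inference.

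**4. Size of the fall, if it is one score.** The documents give no NPI mean, SD or retest correlation, so all of the following are assumptions:
- Eight skewed source distributions, capped at 144: gamma with mean/SD 10/10, 15/12 and 20/15; lognormal with median/log-SD 8/0.6, 8/0.8, 12/0.8, 15/0.6 and 15/0.8.
- Retest correlation 0.7, 0.8 or 0.9, which makes 24 scenarios.
- Selection at NPI ≥ 10, no treatment effect, and 20,000 simulated trials of 20 patients in each scenario.

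In five of the eight distributions (15 scenarios) 58-75% of the source population would qualify. In the other three only 35-39% would. The first group is probably more relevant, because recruitment targets patients who already have behavioral symptoms.

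| | 58-75% qualify (15 scenarios) | all 24 |
|---|---|---|
| Fall, points | 0.2 to 1.8 | 0.2 to 2.7 |
| Median d | 0.07 | 0.09 |
| Expected d above 0.154 | 1 of 15 | 6 of 24 |
| PP ≥ 0.75 for benefit | about 31% to 52%, median about 37% | about 31% to 68%, median 41% |
| PP ≥ 0.97 for benefit (nominal 3%) | median 6% | 4% to 25% |
| PP ≥ 0.75, with 1 point of worsening | median 22%; 10 of 15 at or below 25% | 10% to 53%, median 24% |

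One scenario by hand: gamma 15/12, correlation 0.8 (58% qualify). The fall is 1.16 points and the SD of change 9.16, so d = 1.16/9.16 = 0.127. The noncentrality is 0.127 × 4.472 = 0.57. The chance that a noncentral t(19) exceeds 0.688 is about 46%, as simulated. With 1 point of worsening the net fall is 0.16 points and the simulated chance is 27%. With 2 points it is 14%.

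**5. Medication.** No arithmetic applies. Set side by side, the stability rule covers the month before entry, the recording covers baseline, and nothing covers Weeks 2 to 12.

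**The case against.** The strongest case against the point is that its premise is unconfirmed and its likely size small. Both parts stand. The documents never say that the eligibility and baseline NPI are one assessment. In the more relevant scenarios the median d is 0.07, the chance of meeting the rule rises by about 12 percentage points (37% against 25%), and 1 point of natural worsening takes the median below nominal.

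The low bar of d = 0.15 is also a feature of the threshold and would exist without any selection. The paired t approximation only approximates the multilevel models that the plan specifies. Normal distributions with correlations of 0.5 to 0.9 give larger figures (39% to 94%), which shows how far the size depends on assumed inputs.

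It can also be said that the plan is open about its design: open-label, non-randomized, 20 patients, efficacy secondary. That is so, and removing regression to the mean would not establish efficacy, since the NPI is informant-based and there is no control. But the plan still names efficacy as an objective and grades the evidence for it, without saying that the graded quantity is uncontrolled change. That part of the concern is not answered.

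A reader might infer that the rule is two-sided, met whenever change differs from zero. It is directional: the probability that a parameter lies above zero, or below it.

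**Conclusion.** The point holds as a limit on interpreting the secondary efficacy result. If the qualifying NPI is the baseline NPI, part of any fall is expected without treatment, and the plan's rule would count it toward efficacy. On the stated assumptions, with 58-75% of source patients qualifying, the fall is about 0.2 to 1.8 points, and PP ≥ 0.75 for benefit occurs in about 31% to 52% of trials with no effect, against 25% without selection. The true size cannot be found from the documents.

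Stronger conclusions are not supported. A reader might infer that the efficacy result must be biased toward benefit, but natural worsening can offset the fall, so the net direction is uncertain. A reader might infer that unrecorded drug changes favor tDCS, but their direction and size are unknown. A reader might infer that the trial's main conclusions are at risk, but acceptability and safety are the primary objectives and neither depends on NPI change. The power figure is arithmetically correct. The changes below are worth making because they are cheap and the medication data may not be recoverable afterwards.

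**What to change.** 1. Add a medication-change question to the existing Week 2, 4, 6 and 12 assessments. Report NPI change with and without participants whose psychotropics changed, labelled as a sensitivity analysis that conditions on a post-baseline event.
2. State under Statistics that NPI change and its posterior-probability labels describe uncontrolled change from baseline, which may include regression to the mean, and are not evidence of tDCS efficacy.
3. State whether the eligibility NPI and the baseline NPI are the same assessment. If a separate, earlier eligibility NPI exists, measure change from the later baseline score. This corrects nothing if they are one score. If correlation decays with time it corrects only part: with correlation to the eligibility score of 0.9 at baseline and 0.8 at Week 6, (0.9 − 0.8)/(1 − 0.8) = half of the shift remains.

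I would not add a table of assumed regression-to-the-mean shifts to the trial report, because its inputs are not in the documents and no conclusion would depend on it.

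Cost: one extra question at each of four existing assessments and a few sentences of text, with no added visits or staff. The downsides are a less favorable efficacy statement and a sensitivity analysis that is itself open to selection.
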